6.7.2. Medical History

Medical history, including details regarding illnesses and allergies, date(s) of onset, and whether condition(s) is currently ongoing, and medication history will be collected on all subjects during screening.

6.7.3. Complete Physical Examination

A physical examination must include source documentation of general appearance, and the following body systems: Head, neck, and thyroid; eyes, ears, nose, throat, mouth, and tongue; chest (excluding breasts); respiratory; cardiovascular; lymph nodes; abdomen; skin, hair, nails; musculoskeletal; neurological.

6.7.4. Vital Signs

Assessment of vital signs will include measurement of resting blood pressure, pulse, respiratory rate, and temperature.

Blood pressure will be measured using the following standardized process:

- Subject should sit for ≥ 5 minutes with feet flat on the floor and measurement arm supported so that the midpoint of the manometer cuff is at heart level;
- Use a mercury sphygmomanometer or automatic blood pressure device with an appropriately sized cuff with the bladder centered over the brachial artery;
- Measure and record the blood pressure to the nearest 2 mmHg mark on the manometer or to the nearest whole number on an automatic device.

6.7.5. 12-Lead ECG

Subjects will be required to rest in a supine position for ≥ 5 minutes prior to making a recording. The investigator (or qualified designee) should review the ECG traces recorded in real time for clinically significant abnormalities.

6.7.6. Creatinine Clearance

Creatinine clearance is calculated by the Cockcroft-Gault equation {Cockcroft 1976} using actual body weight (ABW).

Male:
$$CL_{cr} (mL/min) = [\underline{140 - age (years)}] \times ABW(kg)$$

 $72 \times S_{cr}$

Female:
$$CL_{cr} (mL/min) = [140 - age (years)] \times ABW(kg) \times 0.85$$

 $72 \times S_{cr}$

 $S_{cr} = serum creatinine (mg/dL)$

6.7.7. HCV Resistance Sample

Plasma samples will be collected at Day 1 and at on-treatment visits at Weeks 2, 4, 8, and 12, early termination (if applicable), and all posttreatment visits and may be archived for viral sequence analysis. At any unscheduled visit initiated for the purpose of confirming virologic breakthrough, a viral sequence analysis plasma sample must be collected.

Details regarding the collection, processing, and shipping of samples will be included in the lab manual.

6.7.8. HBV DNA Sample

A sample for HBV DNA testing will be collected at on-treatment visits at Weeks 2, 4, 8, and 12 or early termination (if applicable) and posttreatment week 4. HBV DNA will only be tested when ALT > 2x Day 1 value in subjects who are HBsAb or HBcAb positive at Screening.

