3.4.1. Toxicity-Based Stopping Criteria

The Medical Monitor must be consulted prior to dose discontinuation of SOF/VEL FDC unless the investigator believes that immediate action is warranted to ensure the continued safety of the subject.

Due to a clinical or laboratory event, administration of study drug may be discontinued. There is no option for SOF/VEL FDC dose reduction. If SOF/VEL FDC is stopped due to toxicity, it must not be restarted. In these cases that study drug is discontinued permanently, the subject must complete an ET visit. Posttreatment Week 4, 12, and 24 visits must also be scheduled, 4, 12, and 24 weeks from the last dose of study drug.

Subjects who meet any of the following laboratory criteria must stop all study drug:

- Elevation of ALT and/or AST above the upper limit of normal and > 5x Day 1 or nadir, confirmed by immediate repeat testing
- Abnormal elevation of ALT > 3 x Day 1 *and* total bilirubin > 2 x ULN, confirmed by immediate repeat testing
- Elevation of ALT > 15 x ULN, confirmed by immediate repeat testing
- Any Grade 3 or greater rash associated with constitutional symptoms
- Any Grade 4 adverse event or laboratory abnormality assessed (and confirmed by immediate repeat testing) as related to SOF/VEL FDC

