6.7. Procedures and Specifications

6.7.1. Clinical Laboratory Analytes

Hematology: Hematocrit, Hemoglobin (Hb), Platelet count, Red blood cell count (RBC), White blood cell count (WBC) with differential (absolute and percentage) including Lymphocytes, Monocytes, Neutrophils, Eosinophils, and Basophils, Reticulocyte count and mean corpuscular volume (MCV).

Coagulation: INR, Prothrombin Activation %, Prothrombin time (PT), Activated partial thromboplastin time (aPTT)

Chemistry: Alanine aminotransferase (ALT/SGPT), Aspartate aminotransferase (AST/SGOT), Albumin, Alkaline phosphatase, Creatine Kinase, Creatinine, Direct Bilirubin, Total Bilirubin, Glucose, Lipase, Potassium, Sodium, phosphate, uric acid, FibroTest[®] (at Screening only)

Urinalysis: Blood, Glucose, Leukocyte esterase, pH, Protein, Urobilinogen. Reflex to microscopic urinalysis if dipstick result is abnormal.

Virological Tests: Serologies for HCV and HBV. HBV DNA (reflex testing done when ALT > 2x Day 1 value in subjects who are HBsAb or HBcAb positive at Screening). Serology and/or antigen testing for HIV, including reflex testing as necessary. HCV RNA will be measured using the COBAS[®] AmpliPrep/COBAS[®] TaqMan[®] HCV Quantitative Test,

version 2.0. HCV genotype and subtype will be determined using the Siemens VERSANT® HCV Genotype INNO-LiPA2.0 Assay. Gilead reserves the right to use alternate assays for HCV RNA and HCV genotype should the above assays become unavailable or are not definitive.

IL28B genotype will be determined by polymerase chain reaction (PCR) amplification of the SNP, rs12979860, with sequence specific forward and reverse primers and allele specific fluorescently labeled TaqMan® MGB probes. Gilead reserves the rights to use an alternate assay for IL28B determination should the above assay become unavailable.

Pregnancy Tests: Serum β-hCG or Urine β-hCG (if positive, requires immediate confirmation with Serum β-hCG), and serum FSH.

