7.1.2. Serious Adverse Events

A **serious adverse event** (SAE) is defined as an event that, at any dose, results in the following:

- Death
- Life-threatening (Note: The term "life-threatening" in the definition of "serious" refers to an event in which the subject was at risk of death at the time of the event; it does not refer to an event that hypothetically might have caused death if it were more severe.)
- In-patient hospitalization or prolongation of existing hospitalization

- Persistent or significant disability/incapacity
- A congenital anomaly/birth defect
- A medically important event or reaction: such events may not be immediately life-threatening or result in death or hospitalization but may jeopardize the subject or may require intervention to prevent one of the other outcomes constituting SAEs. Medical and scientific judgment must be exercised to determine whether such an event is a reportable under expedited reporting rules. Examples of medically important events include intensive treatment in an emergency room or at home for allergic bronchospasm; blood dyscrasias or convulsions that do not result in hospitalization; and development of drug dependency or drug abuse. For the avoidance of doubt, infections resulting from contaminated medicinal product will be considered a medically important event and subject to expedited reporting requirements.

7.1.3. Clinical Laboratory Abnormalities and Other Abnormal Assessments as Adverse Events or Serious Adverse Events

Laboratory abnormalities without clinical significance are not recorded as AEs or SAEs. However, laboratory abnormalities (eg, clinical chemistry, hematology, and urinalysis) that require medical or surgical intervention or lead to IMP interruption, modification, or discontinuation must be recorded as an AE, as well as an SAE, if applicable. In addition, laboratory or other abnormal assessments (eg, electrocardiogram, x-rays, vital signs) that are associated with signs and/or symptoms must be recorded as an AE or SAE if they meet the definition of an AE or SAE as described in Sections 7.1.1 and 7.1.2. If the laboratory abnormality is part of a syndrome, record the syndrome or diagnosis (eg, anemia), not the laboratory result (ie, decreased hemoglobin).

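### HBV DNA testing is triggered only by ALT above twice Day 1, so an HBV-seropositive subject can be stopped for a liver flare without the assay being required

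*Protocol*

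**What the plan says.** **HBV DNA.** Protocol 6.7.8 schedules a sample at Weeks 2, 4, 8 and 12 or early termination (ET), and at posttreatment Week 4. It limits the assay: "HBV DNA will only be tested when ALT > 2x Day 1 value in subjects who are HBsAb or HBcAb positive at Screening". Protocol 6.7.1 gives the same trigger ("reflex testing done when ALT > 2x Day 1 value in subjects who are HBsAb or HBcAb positive at Screening"). Footnote i of Protocol Appendix 2 repeats it with the word only, as does footnote i of SAP Appendix 1.

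**Stopping rules.** Protocol 3.4.1 lists five criteria that require all study drug to stop:

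1. "Elevation of ALT and/or AST above the upper limit of normal" and more than "5x Day 1 or nadir, confirmed by immediate repeat testing".
2. ALT above 3x Day 1 with total bilirubin above 2 x ULN.
3. "Elevation of ALT > 15 x ULN, confirmed by immediate repeat testing".
4. Grade 3 or greater rash with constitutional symptoms.
5. "Any Grade 4 adverse event or laboratory abnormality assessed (and confirmed by immediate repeat testing) as related to SOF/VEL FDC".

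The stop is permanent: "If SOF/VEL FDC is stopped due to toxicity, it must not be restarted".

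**Who can enter.** Protocol 4.3 excludes HBsAg-positive subjects and those with ALT or AST above 10 x ULN at Screening. HBsAb and HBcAb are measured at Screening, but neither is an exclusion.

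**The concern.** The two rules measure a flare against different baselines. Criterion 1 allows for ALT falling below Day 1 and treats a large rebound from that lower level as reason to stop for good. The HBV DNA trigger stays fixed to Day 1 and ignores AST. The further ALT falls on treatment, the larger the rebound that stops the drug without requiring the assay.

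What is at stake is recognition of HBV reactivation in a subject with cirrhosis who has just lost the study treatment. A sample is due at the ET visit, but nothing in the plan requires it to be tested. The documents do not state why HBV DNA samples are drawn; work-up of a flare is inferred from the ALT trigger and the restriction to seropositive subjects.

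**Working it through.** The plan gives no figure on this point to reproduce. The check asks, for each criterion in 3.4.1, whether it can be met while ALT is at or below the test trigger.

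**Notation.** All values are in multiples of ULN: d = Day 1 ALT, n = nadir ALT. The test is required when ALT > 2d (6.7.8). The values of d and n below are assumed, because the documents give no ALT distribution. Grade 4 ALT or AST is > 10 x ULN (Protocol Appendix 3).

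**Criterion 1, ALT against Day 1.** The stop needs ALT > 5d. Since 5d > 2d, the test is always triggered. No gap.

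**Criterion 1, ALT against nadir.** The stop applies above max(1, 5n), so the gap runs from there up to 2d. It exists when 2d > 1 and 2d > 5n, that is, d > 0.5 and n < 0.4d: a fall of more than 60%.

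| d | n | Stop above | Test above | Stop without required test |
|---|---|---|---|---|
| 1 | 0.5 | 2.5 | 2 | none |
| 1.5 | 0.5 | 2.5 | 3 | 2.5 to 3 |
| 2 | 0.5 | 2.5 | 4 | 2.5 to 4 |
| 3 | 0.5 | 2.5 | 6 | 2.5 to 6 |
| 2 | 1.0 | 5 | 4 | none |
| 3 | 1.0 | 5 | 6 | 5 to 6 |

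In laboratory units, assuming ULN = 40 U/L, Day 1 = 150 and nadir = 25: the stop applies above 5 × 25 = 125 U/L and the test above 2 × 150 = 300 U/L.

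**Criterion 1, AST alone.** AST above ULN and > 5x its own Day 1 or nadir is enough to stop. The trigger contains no AST term, so ALT need never pass 2d.

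**Criterion 2.** ALT > 3d already exceeds 2d. No gap.

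**Criterion 3.** The gap runs from 15 to 2d and needs d > 7.5. At d = 8 it is 15 to 16; at d = 10 it is 15 to 20.

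**Criterion 4.** Rash; not a liver enzyme criterion.

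**Criterion 5, related Grade 4 ALT.** The gap runs from 10 to 2d and needs d > 5. At d = 6 it is 10 to 12; at d = 8, 10 to 16; at d = 10, 10 to 20. A related Grade 4 AST again involves no ALT value.

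**Result.** Criteria 1, 3 and 5 can each be met without the test being required. Within criterion 1, the gap arises only through the ALT nadir and AST-alone routes.

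**The case against.** The strongest reply is that nothing here is an inconsistency. The trigger is stated the same way in four places, both rules can be followed together, and no section says that every liver stop must prompt an HBV assay. That is correct: the point concerns coverage, not contradiction.

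There are also real safeguards. Section 3.4.1 requires immediate repeat testing for the enzyme criteria and Medical Monitor consultation unless immediate action is warranted. The ET visit (6.5) and posttreatment Week 4 (6.3.1) each include chemistry and an HBV DNA sample, so a flare that later passes twice Day 1 triggers the test then. Section 6.6 lets the investigator order clinically indicated assessments at an unscheduled visit, and 7.3 asks for AEs to be followed to resolution or stability where possible. These may well lead to an assay, but none requires it when ALT stays in the gap.

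A reader might infer more than the documents support:

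- **That HBV DNA testing is forbidden outside the trigger.** The restriction in 6.7.8 concerns the protocol sample; 6.6 leaves room for discretionary testing.
- **That the primary safety endpoint is miscounted.** A laboratory abnormality that would "lead to IMP interruption, modification, or discontinuation must be recorded as an AE" (Protocol 7.1.3), and the endpoint in 8.1.2 counts AEs leading to permanent discontinuation whatever their cause. The count is the same with or without the assay.
- **That treatment-related AE rates are biased.** Section 7.2.1 accepts a No on relatedness when there is evidence of another etiology. A negative HBV DNA result would not itself supply that evidence, and the documents do not say how reactivation on study drug should be classed. No size can be attached to this.

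**Conclusion.** The concern holds as a gap in safety monitoring. Followed as written, the plan permits a permanent stop for a liver flare in an HBsAb- or HBcAb-positive subject without requiring the HBV DNA assay.

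The nadir route matters most, because it needs only a fall of more than 60% in ALT and a Day 1 value above half of ULN. The ALT routes under criteria 3 and 5 need a high Day 1 ALT, above 7.5 and 5 x ULN respectively, against a Screening cap of 10 x ULN, so they are narrower.

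The threshold comparisons follow from the text alone; the worked bands rest on assumed Day 1 and nadir values. Without an ALT distribution or HBV seroprevalence in the documents, the number affected among about 36 subjects cannot be stated and may be zero. No efficacy result is touched, and the SAP describes no HBV DNA analysis that would change. This is a cheap improvement.

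**What to change.** Amend Protocol 6.7.8, 6.7.1 and Appendix 2 footnote i, and SAP Appendix 1 footnote i, to read:

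> For subjects HBsAb or HBcAb positive at Screening, HBV DNA will be tested when ALT exceeds twice the Day 1 value, or when any ALT or AST criterion in Section 3.4.1 is met, including a Grade 4 ALT or AST being assessed for relatedness.

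Test the sample from the visit at which the criterion is met, or the ET sample. Test earlier samples for reference only if they were retained. Section 6.7.8 says nothing about retention (the archiving provision in 6.7.7 concerns HCV resistance samples), the earliest HBV DNA sample is Week 2, and none is scheduled on Day 1. It should not be assumed that the change can be applied retrospectively to subjects already dosed.

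The cost is a few extra assays, mostly on samples already scheduled, some for flares that prove unrelated to HBV. It also needs a protocol amendment with documented IRB/IEC approval before implementation (Protocol 9.2.1), at approximately 20 planned centers. No new scheduled sample or SAP table is needed.

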6.7.9. Pregnancy Testing

All females of childbearing potential will have a serum pregnancy test at Screening. Urine pregnancy testing will occur at Day 1 and every 4 weeks through posttreatment 4. In the event of a positive urine pregnancy result, subjects will be instructed to return to the clinic as soon as possible for a serum pregnancy test.

6.7.10. IL28B Testing

A blood sample will be obtained at Day 1 for specific genetic analysis of the rs12979860 (IL28B) genetic variant.

6.8. End of Study

Subjects are considered to have completed the study after the posttreatment Week 24 visit, regardless of treatment duration or early termination of study drug.

6.9. Post Study Care

No poststudy ongoing care will be provided.

7. ADVERSE EVENTS

7.1. Definitions of Adverse Events, Adverse Reactions, and Serious Adverse Events

7.1.1. Adverse Events

An adverse event (AE) is any untoward medical occurrence in a clinical study subject administered a medicinal product, which does not necessarily have a causal relationship with the treatment. An AE can therefore be any unfavorable and/or unintended sign, symptom, or disease temporally associated with the use of a medicinal product, whether or not considered related to the medicinal product. AEs may also include pre- or post-treatment complications that occur as a result of protocol specified procedures, lack of efficacy, overdose, drug abuse/misuse reports, or occupational exposure. Preexisting events that increase in severity or change in nature during or as a consequence of participation in the clinical study will also be considered AEs.

An AE does not include the following:

- Medical or surgical procedures such as surgery, endoscopy, tooth extraction, and transfusion. The condition that led to the procedure may be an adverse event and must be reported.
- Pre-existing diseases, conditions, or laboratory abnormalities present or detected before the screening visit that do not worsen
- Situations where an untoward medical occurrence has not occurred (eg, hospitalization for elective surgery, social and/or convenience admissions)
- Overdose without clinical sequelae (see Section 7.5.1)
- Any medical condition or clinically significant laboratory abnormality with an onset date before the consent form is signed and not related to a protocol-associated procedure is not an AE. It is considered to be pre-existing and should be documented on the medical history eCRF.

7.1.2. Serious Adverse Events

A **serious adverse event** (SAE) is defined as an event that, at any dose, results in the following:

- Death
- Life-threatening (Note: The term "life-threatening" in the definition of "serious" refers to an event in which the subject was at risk of death at the time of the event; it does not refer to an event that hypothetically might have caused death if it were more severe.)
- In-patient hospitalization or prolongation of existing hospitalization

- Persistent or significant disability/incapacity
- A congenital anomaly/birth defect
- A medically important event or reaction: such events may not be immediately life-threatening or result in death or hospitalization but may jeopardize the subject or may require intervention to prevent one of the other outcomes constituting SAEs. Medical and scientific judgment must be exercised to determine whether such an event is a reportable under expedited reporting rules. Examples of medically important events include intensive treatment in an emergency room or at home for allergic bronchospasm; blood dyscrasias or convulsions that do not result in hospitalization; and development of drug dependency or drug abuse. For the avoidance of doubt, infections resulting from contaminated medicinal product will be considered a medically important event and subject to expedited reporting requirements.

7.1.3. Clinical Laboratory Abnormalities and Other Abnormal Assessments as Adverse Events or Serious Adverse Events

Laboratory abnormalities without clinical significance are not recorded as AEs or SAEs. However, laboratory abnormalities (eg, clinical chemistry, hematology, and urinalysis) that require medical or surgical intervention or lead to IMP interruption, modification, or discontinuation must be recorded as an AE, as well as an SAE, if applicable. In addition, laboratory or other abnormal assessments (eg, electrocardiogram, x-rays, vital signs) that are associated with signs and/or symptoms must be recorded as an AE or SAE if they meet the definition of an AE or SAE as described in Sections 7.1.1 and 7.1.2. If the laboratory abnormality is part of a syndrome, record the syndrome or diagnosis (eg, anemia), not the laboratory result (ie, decreased hemoglobin).

7.2. Assessment of Adverse Events and Serious Adverse Events

The investigator or qualified subinvestigator is responsible for assessing AEs and SAEs for causality and severity, and for final review and confirmation of accuracy of event information and assessments.

7.2.1. Assessment of Causality for Study Drug and Procedures

The investigator or qualified subinvestigator is responsible for assessing the relationship to IMP therapy using clinical judgment and the following considerations:

- No: Evidence exists that the adverse event has an etiology other than the IMP. For SAEs, an alternative causality must be provided (eg, pre-existing condition, underlying disease, intercurrent illness, or concomitant medication).
- Yes: There is reasonable possibility that the event may have been caused by the investigational medicinal product.

It should be emphasized that ineffective treatment should not be considered as causally related in the context of adverse event reporting.

The relationship to study procedures (eg, invasive procedures such as venipuncture or biopsy) should be assessed using the following considerations:

- No: Evidence exists that the adverse event has an etiology other than the study procedure.
- Yes: The adverse event occurred as a result of protocol procedures, (eg, venipuncture)

7.2.2. Assessment of Severity

The severity grading of AEs will be assessed as Grade 1, 2, 3, or 4 using the GSI Grading Scale for Severity of Adverse Events and Laboratory Abnormalities (Appendix 3). For AEs associated with laboratory abnormalities, the event should be graded on the basis of the clinical severity in the context of the underlying conditions; this may or may not be in agreement with the grading of the laboratory abnormality.

7.3. Investigator Requirements and Instructions for Reporting Adverse Events and Serious Adverse Events to Gilead:

Requirements for collection prior to study drug initiation: After informed consent, but prior to initiation of study medication, the following types of events should be reported on the case report form (eCRF): All SAEs, and adverse events related to protocol-mandated procedures.

Adverse Events

Following initiation of study medication, collect all AEs, regardless of cause or relationship, until 30-days or after last administration of study IMP must be reported to the eCRF database as instructed.

All AEs should be followed up until resolution or until the adverse event is stable, if possible. Gilead Sciences may request that certain AEs be followed beyond the protocol defined follow up period.

Serious Adverse Events

All SAEs, regardless of cause or relationship, that occurs after the subject first consents to participate in the study (ie, signing the informed consent) and throughout the duration of the study, including the protocol-required posttreatment follow-up period, must be reported to the eCRF database and Gilead Pharmacovigilance & Epidemiology (PVE) as instructed. This also includes any SAEs resulting from protocol-associated procedures performed after informed consent is signed.

Investigators are not obligated to actively seek SAEs after the protocol defined follow up period; however, if the investigator learns of any SAEs that occur after study participation has concluded and the event is deemed relevant to the use of IMP, he/she should promptly document and report the event to Gilead PVE.

Prior treatment history is collected as part of the study entry criteria and evaluation of individual patient characteristics and will not be generating lack of effect reports as this is outside the scope of the present clinical study. However, investigators should report any cases of lack of effect that they feel appropriate regarding the previous treatment regimen as spontaneous reports to the relevant authorities or marketing authorisation holders.

• All AEs and SAEs will be recorded in the eCRF database within the timelines outlined in the eCRF completion guideline.

Electronic Serious Adverse Event (eSAE) Reporting Process

- Site personnel record all SAE data in the eCRF database and from there transmit the SAE information to Gilead PVE within 24 hours of the investigator's knowledge of the event. Detailed instructions can be found in the eCRF completion guidelines.
- If for any reason it is not possible to record the SAE information electronically, ie, the eCRF database is not functioning, record the SAE on the paper serious adverse event reporting form and submit within 24 hours to:

Gilead PVE: Fax: PPD E-mail: PPD

- As soon as it is possible to do so, any SAE reported via paper must be transcribed into the eCRF Database according to instructions in the eCRF completion guidelines.
- If an SAE has been reported via a paper form because the eCRF database has been locked, no further action is necessary.
- For fatal or life-threatening events, copies of hospital case reports, autopsy reports, and other documents are also to be submitted by e-mail or fax when requested and applicable.
 Transmission of such documents should occur without personal subject identification, maintaining the traceability of a document to the subject identifiers.
- Additional information may be requested to ensure the timely completion of accurate safety reports.
- Any medications necessary for treatment of the SAE must be recorded onto the concomitant medication section of the subject's eCRF and the event description section of the SAE form.

